4.6.4.2. Hypoglycemic events

The following hypoglycemic events (HEs) will be summarized respectively:

- Level 1 hypoglycemia
 - Glucose <70 mg/dL (<3.9 mmol/L) and \geq 54 mg/dL (\geq 3.0 mmol/L)
 - Level 1 hypoglycemia can alert a person to take action such as treatment with fastacting carbohydrates. Providers should continue to counsel participants to treat hypoglycemia at this glucose alert value.
- Level 2 hypoglycemia
 - Glucose <54 mg/dL (<3.0 mmol/L)
 - Level 2 hypoglycemia is also referred to as documented or BG-confirmed hypoglycemia with glucose <54 mg/dL (<3.0 mmol/L). This glucose threshold is clinically relevant regardless of the presence or absence of symptoms of hypoglycemia.
- Level 3 hypoglycemia (Severe)

- A severe hypoglycemic event is characterized by altered mental or physical status requiring assistance of another person to actively administer carbohydrate, glucagon, or other resuscitative actions for the treatment of hypoglycemia.
- The determination of an episode of severe hypoglycemia is made by the investigator based on the medical need of the participant to have required assistance and is not predicated on the report of a participant simply having received assistance. Those hypoglycemic events for which the answer is "yes" to the question "Did the subject experience a severe hypoglycemic episode with neurological (cognitive) impairment requiring assistance?" on the Hypoglycemic Events eCRF page and/or it is recorded as a SAE will be classified as Level 3.
- Severe hypoglycemia
 - A severe hypoglycemic event is characterized by altered mental or physical status requiring assistance of another person to actively administer carbohydrate, glucagon, or other resuscitative actions for the treatment of hypoglycemia
 - Examples of severe hypoglycemia in adults are
 - altered mental status and the inability to assist in their own care
 - semiconscious or unconscious, or
 - coma with or without seizures.
- Nocturnal hypoglycemia
 - Nocturnal hypoglycemia is a hypoglycemia event, including severe hypoglycemia, which occurs at night and presumably during sleep.
 - Defined as a hypoglycemia event, including severe hypoglycemia, which occurs at night and presumably during sleep. If for a hypoglycemia event the answer to the question "When did the hypoglycemic event occur?" is "Between bedtime and waking (while asleep)" on the Hypoglycemic Events eCRF page, then that event will be classified as nocturnal hypoglycemia.

To avoid duplicate reporting, all consecutive BG values occurring within a 1-hour period may be considered to be a single hypoglycemic event and the one with the lowest BG value can be selected to be the representative. If two records with the same lowest values within a hour, the earlier occurrence will be selected.

Statistical summaries and analyses will exclude hypoglycemic events occurring after initiation of a new antihyperglycemic therapy. For severe hypoglycemia and level 2 hypoglycemia incidence as well as rate per patient per year of exposure will be provided at specified time intervals.

For each HEs defined above, the total number of the respective HEs occurring between Week -3 and Day 1 will be used to calculate baseline frequency of total HEs respectively. Similarly, for each HEs defined above, the total number of respective HEs occurring in the 14 calendar days prior to Visit 3 (Week 4), Visit 4 (Week 8), and Visit 5 (Week 12) will be used to calculate frequency of total HEs for each HE defined above at each visit respectively.

Hypoglycemia events will be summarized by descriptive statistics. Summaries will include the number and percentage of participants experiencing at least 1 event and the total number of events for each visit. Where possible, the summaries will be presented by Level as well.

The incidence of hypoglycemic event will be analyzed using logistic regression with baseline HbA1c category ($\leq 8.0\%$, >8.0%) as fixed effects.

The rate of hypoglycemic episodes per patient month may be analyzed using a generalized linear MMRM assuming the number of hypoglycemic episodes follows a negative binomial distribution with the mean modeled using visits and baseline HbA1c category ($\leq 8.0\%$, > 8.0%) as fixed effects if data warrants. The logarithm of months in specified time interval will be adjusted as an offset to account for possible unequal treatment duration in the specified time interval between patients. When the number of hypoglycemic events is less than 10, the listing of hypoglycemic events will be provided instead.

Data collected on the Hypoglycemic Events CRF page will be presented in listings.

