Visit Interval Tolerance (Days)	+3/-7	0	±3	±3	±3		Flexibility is built into the screening visit to ensure adequate CGM session and appropriate timing for stopping the baseline GLP-1 RA and initiating tirzepatide at Visit 2; see Section 4.1.1.
Fasting Visit		Х			Х	Х	
Study intervention injection training with demo device		Х					Train participant with demo device prior to initial injection.
Review hypoglycemic events collected in the diary		Х	Х	Х	Х	Х	
Participant Diary							
Participant diary dispensed	Х	Х	Х	Х			Diary includes blood glucose values, collection of intervention administration, information on dosing date/time, and hypoglycemia. See Section 8.1.
Diary compliance check		Х	Х	Х	Х	Х	
Diary return		Х	Х	Х	Х	Х	
Laboratory Tests and Sample Collections							
Hematology	Х						
Hemoglobin A1C (HbA1c)	Х	Х	Х	Х	Х	Х	

GPIL	
l	
I8F-N	

Study 18F-MC-GP1L	Period I -   Screening	Period II -	Treatment	Period			Comments
Visit Number	1	2	3	4	5	ED	ED = carly discontinuation
Week Relative to Study Intervention Start	-3	0	4	8	12		
Visit Interval Tolerance (Days)	+3/-7	0	±3	士3	±3		Flexibility is built into the screening visit to ensure adequate CGM session and appropriate timing for stopping the baseline GLP-1 RA and initiating tirzepatide at Visit 2; see Section 4.1.1.
Fasting Visit		Х			Х	Х	
Clinical chemistry	Х	Х			Х	Х	Includes glucose testing.
Lipid panel		Х			Х	Х	
Urinalysis	Х						
Serum pregnancy	Х						Only for WOCBP and females with a history of tubal ligation. See Section 10.4.2.
Urine pregnancy (local)		Х			Х	Х	Collect for WOCBP only. The result must be available prior to first dose of intervention. Perform additional pregnancy tests if there is clinical suspicion of pregnancy, or as required by local law or regulation.
Follicle stimulating hormone (FSH)	X						Optional; perform as needed to confirm postmenopausal status. See Section 10.4.
Calcitonin	Х						

ЪЦ
Ģ
1Ċ
[8F-N

Study I8F-MC-GPIL	Period I - Screening	Period II -	Treatment	Period			Comments
Visit Number	1	2	3	4	5	ED	ED = early discontinuation
Week Relative to Study Intervention Start	-3	0	4	8	12		
Visit Interval Tolerance (Days)	+3/-7	0	±3	±3	±3		Flexibility is built into the screening visit to ensure adequate CGM session and appropriate timing for stopping the baseline GLP-1 RA and initiating tirzepatide at Visit 2; see Section 4.1.1.
Fasting Visit		Х			Х	Х	
Estimated glomerular filtration rate (eGFR)	Х						Calculate using CKD-EPI method.
Urinary albumin/creatinine ration (UACR)	Х						

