### 8.3.3.6. Hypoglycemia

Participants will be trained by authorized study personnel about signs and symptoms of hypoglycemia, how to treat hypoglycemia, and how to collect appropriate information for each episode of hypoglycemia in the study according to the SoA (Section 1.3). Site personnel will enter this information into the eCRF at each visit.

To avoid duplicate reporting, all consecutive BG values  $\leq$ 70 mg/dL (3.9 mmol/L) occurring within 1-hour period may be considered to be a single hypoglycemic event (Weinberg et al. 2010; Danne et al. 2013).

CGM data will not be used to evaluate hypoglycemia.

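### By-visit hypoglycemia counts set a nominal 21-day baseline against 14-day post-switch windows that cover half the treatment period, and no time divisor is stated

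*SAP*

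**What the plan says.** SAP 4.6.4.2 sets two counting rules, applied to each hypoglycemia category. At baseline, "the total number of the respective HEs occurring between Week -3 and Day 1 will be used to calculate baseline frequency of total HEs". After the switch it uses "the total number of respective HEs occurring in the 14 calendar days prior to Visit 3 (Week 4"), and likewise before Visits 4 and 5. Neither rule gives a formula, unit or divisor for frequency. A later paragraph describes the by-visit output: "Summaries will include the number and percentage of participants experiencing at least 1 event and the total number of events for each visit". That paragraph names no window.

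The same section has some time-adjusted output. For severe and Level 2 events, "incidence as well as rate per patient per year of exposure will be provided at specified time intervals", but those intervals are never defined. For episodes in general, "The rate of hypoglycemic episodes per patient month may be analyzed using a generalized linear MMRM", with an offset for log months; this model is optional and depends on the data. In addition, "Statistical summaries and analyses will exclude hypoglycemic events occurring after initiation of a new antihyperglycemic therapy".

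SAP 4.1 ties all safety analyses to the visit windows of Table 1 (Days 2-43, 44-81 and 82-88). SAP 1 places the table specifications in a separate document.

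In the Protocol 1.3 Schedule of Activities, the diary is first dispensed at Visit 1: "Diary includes blood glucose values, collection of intervention administration, information on dosing date/time, and hypoglycemia". Visit 1 is set at Week -3 with a tolerance of +3/-7 days, and Visits 3 to 5 have ±3 days.

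**The concern.** The by-visit table will place baseline beside Weeks 4, 8 and 12, and readers will compare the columns. Raw event counts, and the share of participants with at least one event, both grow with the number of days counted. A longer baseline window therefore makes hypoglycemia appear to fall after the switch even if the rate has not changed.

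The post-switch windows also omit the first two weeks. Protocol 6.5 says the study is designed to assess the move from a GLP-1 RA to tirzepatide 5 mg, so the by-visit summary leaves out the period immediately after that move.

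**Working it through.** The plan gives no figure of its own to reproduce, so the check is window arithmetic.

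**Inputs.** Screening is nominally 3 weeks = 21 days (SAP 1.2). The screening tolerance is +3/-7 days and the Visit 3 tolerance is ±3 days (Protocol 1.3). Target days are 29, 57 and 85 (SAP Table 1). Post-switch windows are 14 days (SAP 4.6.4.2).

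**1. Count ratio with an unchanged rate** = 14 / baseline days.

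| Baseline days | Basis | Post/baseline ratio |
|---|---|---|
| 21 | nominal | 14/21 = 0.67 |
| 22 | nominal, Day 1 included | 14/22 = 0.64 |
| 18 to 28 | tolerance moves the date of Visit 1 | 14/18 = 0.78 to 14/28 = 0.50 |
| 14 to 24 | tolerance sign read the other way | 14/14 = 1.00 to 14/24 = 0.58 |

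**2. Participants with at least one event.** The documents give no event rate, so rates are assumed. With Poisson events, P = 1 - exp(-rate × days / 365.25):

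| Assumed rate per patient-year | 21 days | 14 days |
|---|---|---|
| 0.5 | 2.83% | 1.90% |
| 1 | 5.59% | 3.76% |
| 2 | 10.86% | 7.38% |
| 5 | 24.98% | 17.44% |

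The ratio of the two percentages is 0.67 to 0.70. Percentages do not repair the mismatch: the default denominator in SAP 4.1 is everyone in the analysis set.

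**3. Coverage after the switch.** At target days the windows are Days 15-28, 43-56 and 71-84, or 3 × 14 = 42 of 84 days. Days 1-14, 29-42 and 57-70 fall outside. With Visit 3 on Day 26 the window is Days 12-25, so Days 1-11 are omitted. With Visit 3 on Day 32 it is Days 18-31, so Days 1-17 are omitted.

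**4. Table 1 applied instead.** Days 2-43 span 42 days, Days 44-81 span 38 and Days 82-88 span 7. Against a 21-day baseline an unchanged rate gives 42/21 = 2.00, 38/21 = 1.81 and 7/21 = 0.33.

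**5. After the change below.** Dividing each count by its own days brings the constant-rate ratio to 1.00. Intervals of Days 1-28, 29-56 and 57-84 cover 84 of 84 days.

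**Separate minor check: exposure.** SAP 4.6.1 counts last dose minus first dose plus 1. Twelve weekly doses on schedule (Days 1 to 78) give 78 - 1 + 1 = 78 days, below the 84 needed for the category of at least 12 weeks.

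**The case against.** The ratio of 0.67 depends on reading frequency as an undivided count. The totals are inputs to a frequency, the same section uses per-year rates and an offset elsewhere, and the table shells might supply a divisor. That is fair, but as written the SAP permits either a count or a rate, and total events per visit is a count on any reading.

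The by-visit paragraph names no window, so Table 1 could govern it and Days 2-14 would then be covered. The wording conflict is real. Step 4 shows that this reading only exchanges one mismatch for another.

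A reader might infer that early events are lost. They are not. All events are listed. Protocol 8.3.3.6 requires severe events to be reported as SAEs, so they enter the TEAE and SAE tables, which use no visit windows. Severe and Level 2 events have per-year rates, and the logistic incidence analysis is not limited to 14 days. Protocol 9.3.5.1 does not require a rate for every category. Events may also be few: the permitted oral agents exclude sulfonylureas, and with fewer than 10 events the SAP falls back on a listing.

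Two other readings are tempting.

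- A 12-day screening period would give 14/12 = 1.17 and reverse the direction. But 12 days is the minimum in Protocol 4.1.1 for adequate CGM data, and it lies outside both readings of the visit tolerance (18-28 or 14-24 days).
- The 14 days might seem borrowed from the CGM session, against the Protocol 8.3.3.6 rule that "CGM data will not be used to evaluate hypoglycemia". But the same window applies at Visit 4, where no scheduled CGM session ends, and the SAP nowhere says CGM data enter these counts.

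On exposure, the number of doses is not stated. A Visit 5 on Days 86-88 may allow a Day 85 dose, which gives 85 days. Nor can the 78-day figure be carried into the per-year hypoglycemia rates, because their denominator is not stated.

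**Conclusion.** The point holds for the by-visit hypoglycemia summary. With frequency read as a count and the rate unchanged, the post-switch count is 0.67 of baseline on the nominal schedule: 0.50-0.78 or 0.58-1.00 across the tolerance, depending on how its sign is read. Under the 14-day rule at target days, half the treatment period is outside the windows, including Days 1-14 (the first 11 to 17 days within the Visit 3 tolerance). The SAP does not say whether the 14-day rule or Table 1 governs, and neither gives comparable columns. Level 1 and nocturnal events have no guaranteed time-adjusted summary.

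The consequence is limited to descriptive safety tables. No test of baseline against post-switch hypoglycemia is specified, and the primary analysis is unaffected. The change should be made because it is cheap and the present rule can mislead. The exposure category is a minor separate note: completers with twelve on-schedule doses would fall short of 12 weeks by definition.

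**What to change.** Revise SAP 4.6.4.2 as follows.

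- For every hypoglycemia category, report events per participant-time.
- At baseline, divide by each participant's actual days from Visit 1 to first dose, and assign Day 1 events by the time of that dose.
- After the switch, use contiguous intervals (first dose to Visit 3, Visit 3 to 4, Visit 4 to 5) and the whole treatment period.
- Name these as the specified time intervals, and state that they override both the 14-day windows and Table 1 for hypoglycemia.
- End time at risk when a new antihyperglycemic therapy starts, to match the exclusion of later events, and name this time as the per-year denominator.

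For exposure in SAP 4.6.1, count the final weekly dosing interval, cap the result at end of participation for everyone, and allow the 3-day Visit 5 tolerance in the 12-week category. For example, twelve on-schedule doses give 78 - 1 + 7 = 84 days, capped at 82 if Visit 5 falls on Day 82. That still qualifies against 84 - 3 = 81.

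The cost is one SAP revision, re-specified table shells and minor programming. The dates needed are already collected in the diary and CRF.

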4.6.4.3. Severe Persistent Hyperglycemia

Defined as Fasting Blood Glucose (via SMBG) >270 mg/dL (>15 mmol/L) during the first 4 weeks or >240 mg/dL (>13.3 mmol/L) from Weeks 5-12 occurring for at least 2 consecutive weeks. The number and percentage of participants with severe, persistent hyperglycemia will be summarized and data will be listed.

4.6.4.4. Gastrointestinal Events

The following gastrointestinal events will be summarized respectively:

- Nausea
- Vomiting
- Diarrhea
- Abdominal Pain/Abdominal Cramps
- other

These events are recorded on the "*Hypersensitivity, Anaphylactic and Infusion/Injection Related Reaction Follow-up*" eCRF page. If the answer to the question "Does subject have gastrointestinal signs or symptoms?" is "Yes" then the applicable event type is recorded as well ("Nausea", "Vomiting", "Diarrhea", "Abdominal Pain/Abdominal Cramps", "Other"). The events are defined based on this information. Additionally, this information is linked to the AE page where their severity is also captured.

A summary of the number of gastrointestinal events by severity and event type will be presented in a table, and the number and percentage of participants with at least one event will be provided. The severity that will be presented represents the most extreme severity captured on the CRF page. The possible severities are "*Mild*," "*Moderate*," and "Severe." If a participant reported multiple occurrences of the same event, only the most severe will be presented. Events that are missing severity will be presented in tables as "Severe" but will be presented in the data listing with a missing severity. Percentages will be calculated out of the number of participants in the Safety set. The time courses of prevalence and incidence (newly-occurring episodes) of nausea, vomiting, diarrhea, and combined will be plotted and maximum severity.

The maximum severity and duration of treatment-emergent nausea, vomiting, diarrhea, and combined through the end of the study will be summarized.

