#### 8.3.3.8. Hypersensitivity Reactions

Many drugs, particularly oral agents and biologic agents, carry the risk of systemic hypersensitivity reactions. If such a reaction occurs, additional data should be provided to the sponsor in the designated CRFs.

Sites should have appropriately trained medical staff and appropriate medical equipment available when study participants are receiving study intervention. It is recommended that participants who experience a systemic hypersensitivity reaction be treated per national and international guidelines. In the case of a suspected hypersensitivity event, additional blood samples should be collected as described in Appendix 2, Section 10.2.1. Laboratory results are provided to the sponsor via the central laboratory.

If the investigator determines that a systemic hypersensitivity reaction has occurred related to study intervention administration, the participant may be permanently discontinued from the intervention, and the sponsor's designated medical monitor should be notified. If the investigator is uncertain about whether a systemic hypersensitivity reaction has occurred and whether discontinuation of study intervention is warranted, the investigator may consult the sponsor.

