### 8.3.3.9. Injection-Site Reactions

Symptoms and signs of a local ISR may include erythema, induration, pain, pruritus, and edema.

If an ISR is reported by a participant or study personnel, the ISR CRF will be used to capture additional information about this reaction, for example, injection-site pain, degree and area of erythema, induration, pruritis, and edema.

At the time of AE occurrence in the tirzepatide group, samples will be collected for measurement of tirzepatide anti-drug antibodies and tirzepatide concentration.

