4.6.2. Adverse Events

All adverse events will be classified by System Organ Class (SOC) and Preferred Term (PT) according to the Medical Dictionary for Regulatory Activities. Selected notable AEs of interest may be reported using high-level terms or Standardized Medical Dictionary for Regulatory Activities Queries. As an example, 'renal safety event', defined in the protocol as an AE of interest, is defined by the high-level group term 'Renal disorders (excl nephropathies)'. Please refer to Section 6.3 for the SMQs of interest.

A treatment-emergent AE (TEAE) is defined as an AE that meets any of the following conditions:

- begins on or after the first dose of study intervention
- begins before the first dose of study drug and worsens in severity on or after the first dose of study drug
- is completely missing an onset date and end date
- is completely missing an onset date and the end date is on or after the first dose of study intervention.

An overview summary of the number and percentage of participants with any TEAE, serious TEAE, study drug-related TEAE, study drug-related serious TEAE, TEAE leading to treatment discontinuation, TEAE leading to study termination, and AE leading to death will be provided. The number of events will also be summarized.

Local Adverse Events (i.e., injection site reactions) will be tabulated separately in addition to the overall TEAE tables.

Summaries of the total number of TEAEs and the number and percentage of participants with at least one TEAE will be provided. The number and percentage of participants and the number of events will also be presented by SOC and PT. At each level of participant summarization, a participant is counted once if the participant reported one or more events. Percentages will be calculated out of the number of participants in the SS. The number of events at each level of SOC and PT will also be summarized.

A summary of TEAEs will also be presented in descending order from the SOC with the highest total incidence (that is, summed across treatment group) to the SOC with the lowest total incidence. If the total incidence for any two or more SOCs is equal, the SOCs will be presented in alphabetical order. Within each SOC, the PTs will be presented in alphabetical order.

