4.6.4.5. Hypersensitivity, Anaphylactic and Infusion/Injection Related Reaction Followup

Data collected on Hypersensitivity, Anaphylactic and Infusion/Injection Related Reaction Followup CRF page will be listed. Information to be summarized includes the timing of the reaction relative to study drug administration, and characteristics of the injection site reaction: erythema, induration, pain, pruritis, and edema. Patient based and event-based summaries will be created.

Data collected on this page for gastrointestinal events will be summarized (See Section 4.6.4.4). Additionally, summaries will be created for mucocutaneous, cardiovascular, central nervous system, respiratory and general signs or symptoms in a similar way as for gastrointestinal events. Percentages will be calculated out of the number of participants in the Safety set.

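### The SAP defines GI events from a reaction follow-up eCRF page, so the dedicated GI table may miss ordinary nausea, vomiting and diarrhoea

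*SAP*

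**What the plan says.** SAP 4.6.4.4 lists nausea, vomiting, diarrhoea, abdominal pain or cramps, and other. It says these are recorded on the reaction follow-up eCRF page, through a yes/no question on GI signs or symptoms and an event type. On how that page and the AE page are used: "The events are defined based on this information. Additionally, this information is linked to the AE page where their severity is also captured".

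The section then plans three outputs:
- a table of events and participants by severity and event type;
- plots of prevalence and incidence over time for nausea, vomiting, diarrhoea and the three combined;
- a duration and severity summary: "The maximum severity and duration of treatment-emergent nausea, vomiting, diarrhea, and combined through the end of the study will be summarized".

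SAP 4.6.4.5 describes what the same page holds: "Information to be summarized includes the timing of the reaction relative to study drug administration, and characteristics of the injection site reaction". It refers back to 4.6.4.4 for the page's GI data and extends the method to five other body systems: "summaries will be created for mucocutaneous, cardiovascular, central nervous system, respiratory and general signs or symptoms in a similar way as for gastrointestinal events".

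The protocol collects severe GI AEs on the CRF/AE form (8.3.3.1). In 9.3.5.2 it promises the incidence and severity of nausea, vomiting and diarrhoea, with no restriction to reactions.

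**The concern.** A page made for following up suspected reactions is an unusual source for GI tolerability. Most nausea or diarrhoea on an incretin drug would be reported as an ordinary AE. If no reaction is suspected, there may be no reaction page, and under the SAP's definition the event then does not exist for the dedicated GI table.

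GI tolerability is not a listed objective or endpoint. It is, however, a stated purpose of the study in Protocol 2.1, 4.2 and 6.5.1, because participants start directly at 5 mg. A reader will turn to the table labelled as the GI result. If that table shows fewer affected participants than the general TEAE tables, the report carries two GI results that disagree, with nothing in the SAP to explain why.

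**Working it through.** No figure in the documents tests this point except the planned size of 150, so the check is mainly a reading of the text.

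**1. What the definition includes.** In SAP 4.6.4.4 the event is defined by the page's GI question. The AE page is linked and also captures severity. No sentence adds an AE that lacks an entry on the reaction page.

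**2. When the page is completed.** Neither document says. The available evidence is:
- The title names reactions only.
- Its content in SAP 4.6.4.5 includes reaction timing and injection-site features, which presuppose a reaction.
- Protocol 8.3.3.8, on hypersensitivity: "If such a reaction occurs, additional data should be provided to the sponsor in the designated CRFs".
- Protocol 8.3.3.9: "If an ISR is reported by a participant or study personnel, the ISR CRF will be used to capture additional information about this reaction". The five example characteristics there (pain, erythema, induration, pruritus, edema) are the same five that SAP 4.6.4.5 gives for this page: 5 of 5.

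This points to a page triggered by a suspected reaction, as an inference.

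**3. Whether GI events are defined anywhere else.** SAP 4.6.2 leaves a route open: "Selected notable AEs of interest may be reported using high-level terms or Standardized Medical Dictionary for Regulatory Activities Queries". It is used for renal events (a high-level group term) and, through SMQs, for hepatobiliary, gallbladder and pancreatitis events (4.6.4.6 and 4.6.4.7). For GI symptoms no terms are named, and none of the nine SMQs in Section 6.3 covers them. That is a fact about the list, not proof that no other route exists.

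**4. What is still captured.** SAP 4.6.2 reports all TEAEs: "The number and percentage of participants and the number of events will also be presented by SOC and PT". It also tabulates TEAEs by severity. Ordinary GI AEs therefore remain in the report. Time course and duration have no counterpart in 4.6.2.

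**5. Outputs affected.** Of the three outputs in 4.6.4.4, one (the table by severity and event type) clearly uses the page definition. For the other two the source is unclear.

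**6. Size.** One missed participant changes the table's percentage by 1/150 = 0.67 points, assuming 150 treated. For illustration only, let *p* be the proportion with a GI AE and *c* the proportion of those who also have a reaction page. Both are assumed, since the documents give neither. The table is expected to show 150 × *p* × *c* participants:

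| *p* | Truly affected (150 × *p*) | *c* = 5% | *c* = 25% | *c* = 100% |
|---|---|---|---|---|
| 10% | 15 | 0.75 | 3.75 | 15 |
| 20% | 30 | 1.5 | 7.5 | 30 |
| 30% | 45 | 2.25 | 11.25 | 45 |

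At *p* = 20%, the general tables would show 30/150 = 20%. The dedicated table would show 1.5/150 = 1% at *c* = 5%, or 7.5/150 = 5% at *c* = 25%.

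**The case against.** The strongest objection is that the defect depends on an eCRF page nobody can inspect here. The one direct statement in the SAP is that these GI events are recorded on that page. If sites complete it for every GI AE, nothing is missed. Two of the clues are also indirect: Protocol 8.3.3.8 and 8.3.3.9 do not name the SAP's page, and the injection-site signs they share are standard ones. This stands, and it is why the conclusion is conditional. The page's title and its reaction-timing content are better evidence, and they favour a reaction trigger. Even on the other reading a problem remains: SAP 4.6.4.5 would summarise ordinary nausea as reaction follow-up, with no filter described.

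Second, the general TEAE tables already hold these events, so Protocol 9.3.5.2 is largely met, and a reader could compare the two sets of tables. This also stands. It limits the harm to the dedicated outputs but does not remove the possible disagreement.

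Third, the term treatment-emergent in the duration summary suggests AE data, for which SAP 4.6.2 handles onset and end dates. SAP Section 1 also places table specifications in a separate document, which may name the source. Both are possible, which is why the source of those two outputs is called unclear rather than wrong. A separate specification should not be relied on to override a definition that the SAP states outright.

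Fourth, a single sentence confirming that the page is completed for all GI AEs would be a smaller change. If true, it would settle the undercount, but it would not separate GI tolerability from reaction follow-up or name the source of the plots and duration summary.

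**Conclusion.** The concern holds in conditional form. As written, SAP 4.6.4.4 restricts the GI severity table to events with an entry on the reaction follow-up page. If that page is completed only for suspected reactions, which is the likelier reading but unconfirmed, the table will miss ordinary nausea, vomiting and diarrhoea. The effect runs from none to most of the affected participants, depending on a completion rule that the documents do not give. GI AEs are not lost from the study, and the HbA1c analysis, sample size and power are untouched. It should be fixed, because GI tolerability is part of why the study is run. Confidence is medium, because the eCRF was not available.

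**What to change.** In SAP 4.6.4.4, define nausea, vomiting, diarrhoea and abdominal pain, plus a pre-listed set for the other category, as TEAEs under the 4.6.2 definition, identified by MedDRA preferred term. Take severity and onset and end dates from the AE page. Use this one definition for the severity table, the time-course plots and the duration and maximum-severity summary, and list the terms in Section 6.3.

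Move the present reaction-page method (the question, event type, link to AE severity and counting rules) into 4.6.4.5. Six summaries there rely on it: the page's GI symptoms and the five other body systems. Their references to 4.6.4.4 should then point to the moved text.

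This gives a correct GI table whatever the rule for completing the reaction page. The cost is SAP wording and limited reprogramming of one table, the plots and one summary. No new data are needed, because GI AEs with their severity and dates are already collected on the AE page.
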